1.2.2. Randomization Methodology

As this is a single-agent study, randomization is not applicable.

1.2.3. Stopping Rules and Unblinding

Tagraxofusp treatment could be discontinued for any of the following reasons:

- Patient withdrawal of consent
- Occurrence of unacceptable toxicity, including DLT
- Tagraxofusp related anaphylaxis or Grade ≥ 3 hypersensitivity reaction
- Requirement for >1 dose reduction unless there is evidence of MRD eradication or sustained AML remission (beyond Cycle 2), in which case additional dose reductions are permitted, however these reductions must be discussed with the Medical Monitor and documented in the context of ongoing AML response
- Disease recurrence/progression
- Intercurrent illness that prevents further administration of Tagraxofusp
- Patient non-compliance
- Occurrence of pregnancy
- Completion of 6 cycles of treatment. (The administration of additional cycles of Tagraxofusp [beyond 6 cycles] may be considered in the setting of MRD eradication, sustained AML remission, or other evidence of sustained anti-leukemia benefit in the opinion of the Investigator. Administration of Tagraxofusp beyond 6 cycles must be discussed with the Medical Monitor at which time the individual patient's potential risk/benefit of further treatment will be assessed).
- Investigator's decision

The reason for Tagraxofusp discontinuation and the date of discontinuation are recorded in the electronic case report form (eCRF).

1.2.4. Study Procedures

The schedules of assessments, as outlined in the study protocol, are provided in [Section 7](#), [Table 7-1](#) and [Table 7-2](#).

1.2.5. Efficacy, Pharmacokinetic, and Safety Parameters

1.2.5.1. Efficacy Parameters

Efficacy assessments include rates of MRD eradication (conversion), RFS, and OS. Response/remission will be assessed using International Working Group criteria for AML ([Cheson et al. 2003](#)). Response criteria for AML are summarized in [Section 8.1](#). All efficacy outcomes will be presented by subgroups defined by MRD Status and line of therapy in study (First-Line or Relapsed/Refractory). Definitions for each efficacy assessment are described in [Section 4.3](#).

1.2.5.2. Safety Parameters

Safety evaluations performed during the study included physical examinations, Eastern Cooperative Oncology Group (ECOG) performance status, measurement of vital signs, 12-lead electrocardiograms (ECGs), clinical laboratory evaluations (hematology, serum chemistry, coagulation, and urinalysis), and monitoring of adverse events (AE) (including treatment serious AEs [SAEs]), DLTs, and concomitant medications (CM).

Further details on the definitions and analysis methods for safety endpoints are provided in [Section 4.4](#).

1.2.5.3. Pharmacokinetic and Immunogenicity Parameters

Noncompartmental PK parameter summaries are described in a separate Modeling and Simulation Plan.

Summary of immunogenicity parameters are described in a separate plan.

2. PATIENT POPULATION

2.1. Population Definitions

The following patient populations will be evaluated and used for presentation and analysis of the data:

- Modified Intent-to-Treat (mITT) Population: All patients who are eligible based on the screening criteria and who received at least 1 dose of Tagraxofusp. Patients who meet the criteria for mITT will be considered “evaluable.” Patients will be grouped according to the planned dose level at time of enrollment.
- Safety Population: All patients enrolled in the study who received at least 1 dose of Tagraxofusp. Patients will be grouped according to the actual dose level received.

The mITT population is the primary population for the analysis of efficacy parameters. Supportive subgroup efficacy analyses will be performed in the mITT population, as described in [Section 3.8](#). The safety population is the primary population for the analysis of safety parameters.

2.2. Protocol Violations

All protocol violations will be presented in a data listing.

3. GENERAL STATISTICAL METHODS

3.1. Sample Size Justification

Approximately 21-33 adult patients diagnosed with AML that is considered high-risk disease who have achieved a first or second CR or complete remission with incomplete bone marrow recovery (CRi) within 6 months prior to enrollment and are not considered immediate candidates for allogenic stem cell transplant (SCT). The anticipated sample size is sufficient to evaluate the primary objectives.

During Stage 1, approximately 9-18 patients will be treated with Tagraxofusp.

In Stage 2, up to 20 additional patients with MRD as determined locally will enroll and receive Tagraxofusp at either the MTD or maximum tested dose, so that a total of 15 patients with evidence of MRD, as determined centrally, are treated at this dose. The assumptions governing sample size are as follows:

- Null hypothesis: eradication of MRD $\leq 5\%$
- Alternate hypothesis: eradication of MRD $\geq 20\%$
- Type 1 error: 17% one-sided
- Power: $>80\%$

Because no available anti-leukemia therapies (other than allogeneic transplant) are believed to be associated with the eradication of evidence of MRD in this high-risk AML setting, the study would be considered positive if ≥ 2 of 15 patients in 1st remission are converted from MRD-positive to MRD-negative status. (In a situation where 1 of 15 patients has eradication of MRD, the results may be considered of interest, given the dearth of efficacious therapy in this setting).

At the time of database lock, in Stage 1, 18 patients were enrolled. In Stage 2, 9 patients with MRD were enrolled.

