5.1 Study Population

Approximately 21-33 adult patients diagnosed with AML that is considered high-risk disease who have achieved a first or second CR or complete remission with incomplete bone marrow recovery (CRi) within 6 months prior to enrollment and are not considered immediate candidates for allogenic SCT.

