3.2. General Methods

All data listings that report an evaluation date will include a relative study day (Rel Day). Pre-treatment and on-treatment study days are numbered relative to the day of the first dose of study drug which is designated as Day 1. The preceding day is Day -1, the day before that is Day -2, etc. The last day of study drug is designated with an "L" (eg, Day 26L). Post-treatment study days are numbered relative to the last dose and are designated as Day 1P, Day 2P, etc.

All output will be incorporated into Microsoft Word files, sorted and labeled according to the International Council for Harmonisation (ICH) recommendations, and formatted to the appropriate page size(s).

Tabulations will be produced for appropriate demographic, baseline, efficacy, and safety parameters. For categorical variables, summary tabulations of the number and percentage of patients within each category (with a category for missing data) of the parameter will be presented. Two-sided 95% confidence intervals (CIs) will be computed using the Clopper Exact

method. For continuous variables, the number of patients, mean, median, standard deviation (SD), minimum, and maximum values will be presented. Time-to-event data will be summarized using Kaplan-Meier methodology using 25th, 50th (median), and 75th percentiles with associated 2-sided 95% CIs, as well as percentage of censored observations. Formal statistical hypothesis testing will be performed on a secondary endpoint, eradication or MRD rate among in high-risk AML enrolled in Stage 2.

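### The formal Stage 2 MRD test has no decision rule or operating characteristics for the 9 patients enrolled; the stated 17%, >80% and 2-of-15 belong to n = 15

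*SAP*

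**What the plan says.** SAP 3.1 carries over the design in protocol 11.2: a null MRD-eradication rate of at most 5%, an alternative of at least 20%, "Type 1 error: 17% one-sided", and power above 80%. Stage 2 was to enrol up to 20 patients with locally determined MRD, "so that a total of 15 patients with evidence of MRD, as determined centrally, are treated at this dose". On the decision rule, the study "would be considered positive if ≥ 2 of 15 patients in 1st remission are converted" to MRD-negative status. A single conversion in 15 is described as possibly of interest.

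The section ends with the enrolment achieved: "At the time of database lock, in Stage 1, 18 patients were enrolled. In Stage 2, 9 patients with MRD were enrolled".

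The test itself is kept in SAP 3.2: "Formal statistical hypothesis testing will be performed on a secondary endpoint, eradication or MRD rate among in high-risk AML enrolled in Stage 2". No test statistic, level or cut-off is named there. SAP 3.5 places the efficacy analysis in Stage 2 patients who received 12 µg/kg. SAP 4.3.1 asks only for eradication rates with exact 95% confidence intervals. SAP 5 declares no changes from the protocol's analyses.

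**The concern.** Type I error and power belong to a particular pair of sample size and cut-off. When the sample falls from 15 to 9, neither figure carries over, and a rule expressed as 2 of 15 no longer says what counts as success.

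Two readings are open. One keeps the count at 2 conversions. The other keeps the proportion: 2/15 × 9 = 1.2, which could be taken as 1. As shown in the working, these two rules have very different false-positive risks. The study is open-label, so a cut-off left unstated could be chosen with the results in view.

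This is the only formal test in the SAP and the only criterion for calling the study positive. A reader who sees 0 or 1 conversions needs to know how likely that was under a 20% rate, and the only power figure in the SAP is the one for 15 patients.

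**Working it through.** **Inputs (SAP 3.1).** Null rate p0 = 0.05; alternative p1 = 0.20; planned n = 15 with cut-off r = 2; recorded Stage 2 n = 9.

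**Formula.** The exact binomial probability of at least 2 conversions is P(X ≥ 2) = 1 − (1 − p)^n − n·p·(1 − p)^(n−1). At p0 this is the type I error; at p1 it is the power.

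**Step 1: reproduce the plan's figures, n = 15, r = 2.**
- Type I error: 1 − 0.4633 − 0.3658 = 0.171, the stated 17%.
- Power: 1 − 0.0352 − 0.1319 = 0.833, above the stated 80%.

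The planning figures are therefore right for 15 patients. Neighbouring cut-offs do not match them: r = 1 gives 53.7% and 96.5%; r = 3 gives 3.6% and 60.2%.

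**Step 2: same cut-off, n = 9.**
- Type I error: 1 − 0.6302 − 0.2985 = 0.071.
- Power: 1 − 0.1342 − 0.3020 = 0.564, so the chance of missing a true 20% rate is 1 − 0.564 = 0.436. At n = 15 it was 1 − 0.833 = 0.167.

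**Step 3: other cut-offs at n = 9.**

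| Cut-off | Type I error | Power |
|---|---|---|
| ≥1 of 9 | 37.0% | 86.6% |
| ≥2 of 9 | 7.1% | 56.4% |
| ≥3 of 9 | 0.8% | 26.2% |

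Two is the lowest cut-off with type I error at or below 17%, so 56.4% is the highest power available at n = 9 within that limit. No cut-off gives both stated properties.

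**Step 4: smaller denominators.** The design counts centrally confirmed patients, and the rule is worded for first remission, although protocol 5.2 also admits second remission. SAP 3.1 does not say how many of the 9 meet either condition. The following is illustrative only, with cut-off 2:

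| n | Type I error | Power |
|---|---|---|
| 8 | 5.7% | 49.7% |
| 7 | 4.4% | 42.3% |
| 6 | 3.3% | 34.5% |

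**Step 5: what a low count can exclude.** The exact two-sided 95% upper limit is 33.6% for 0 of 9 and 48.2% for 1 of 9. Both include 20%.

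**The case against.** The strongest reply is that nothing in SAP 3.1 is miscalculated. The section presents 17% and >80% as assumptions behind the sample size, they agree with protocol 11.2, and the shortfall is disclosed in the same section. That stands: a reader might infer an arithmetic error, or a claim of 80% power with 9 patients, and the documents contain neither. What is missing is a rule for the sample that the retained test will use.

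A reader might also infer that 0 or 1 conversions will be reported as a negative finding backed by >80% power. The documents do not say so. SAP 3.1 treats one conversion as possibly of interest, the protocol synopsis adds that further scrutiny would then be needed, and the intervals required by SAP 4.3.1 would show that 20% is not excluded.

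Nor is false-positive control lost if the cut-off stays at 2: 7.1% is below the 17% allowed. Only power suffers.

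It would likewise go too far to say that the 9 are locally positive patients who must shrink after central testing. Local status is plausible from the Stage 2 entry criterion, but the SAP does not specify it, and the planned ratio of 15 to 20 is not an observed confirmation rate.

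Finally, the denominator might be larger than 9. The protocol synopsis includes all patients treated at the MTD or maximum tested dose in efficacy analyses, and SAP 4.3.1 does not restrict the eradication rate to Stage 2. SAP 3.2 and 3.5, however, point to Stage 2, and no count of MRD-positive Stage 1 patients at that dose is given. If pooling is intended, the SAP has to say so and give the number.

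**Conclusion.** The point holds as a gap in the plan. The SAP keeps a formal Stage 2 test, records 9 patients for it, and gives a threshold and error rates only for 15. Keeping the cut-off at 2, power falls from 83.3% to 56.4% and type I error from 17.1% to 7.1%.

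These n = 9 figures rest on two assumptions that the SAP does not state: that the cut-off remains 2, and that all 9 patients count towards the test. Among Stage 2 patients with that cut-off, 56.4% is an upper bound, because any patient not centrally MRD-positive, or excluded by the first-remission wording, lowers it.

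The consequence is limited to a secondary endpoint. The primary objectives, MTD and safety, are untouched. What changes is the inference from fewer than 2 conversions: it cannot be read as evidence of inactivity.

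**What to change.** In SAP 3.1:
- Label 17%, >80% and 2-of-15 as design values for n = 15.
- State the denominator actually evaluable for the test: how many patients are centrally MRD-positive, and whether only first remission counts.
- State the cut-off of at least 2 conversions and its exact type I error and power for that number (for n = 9: 7.1% and 56.4%).
- Commit to reporting the exact one-sided p-value against 5% together with the exact confidence interval.
- State that fewer than 2 conversions is inconclusive and is not evidence of inactivity.

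In SAP 5, record that the rule for the achieved number was set after enrolment closed.

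An acceptable alternative is to drop the formal test in SAP 3.2, report the eradication rate descriptively with its exact confidence interval, and record that as the change in SAP 5.

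The cost is wording in the SAP and the study report, plus a less favourable power figure. No new data or patients are needed.

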3.2. General Methods

All data listings that report an evaluation date will include a relative study day (Rel Day). Pre-treatment and on-treatment study days are numbered relative to the day of the first dose of study drug which is designated as Day 1. The preceding day is Day -1, the day before that is Day -2, etc. The last day of study drug is designated with an "L" (eg, Day 26L). Post-treatment study days are numbered relative to the last dose and are designated as Day 1P, Day 2P, etc.

All output will be incorporated into Microsoft Word files, sorted and labeled according to the International Council for Harmonisation (ICH) recommendations, and formatted to the appropriate page size(s).

Tabulations will be produced for appropriate demographic, baseline, efficacy, and safety parameters. For categorical variables, summary tabulations of the number and percentage of patients within each category (with a category for missing data) of the parameter will be presented. Two-sided 95% confidence intervals (CIs) will be computed using the Clopper Exact

method. For continuous variables, the number of patients, mean, median, standard deviation (SD), minimum, and maximum values will be presented. Time-to-event data will be summarized using Kaplan-Meier methodology using 25th, 50th (median), and 75th percentiles with associated 2-sided 95% CIs, as well as percentage of censored observations. Formal statistical hypothesis testing will be performed on a secondary endpoint, eradication or MRD rate among in high-risk AML enrolled in Stage 2.

3.3. Computing Environment

All descriptive statistical analyses will be performed using SAS statistical software Version 9.4, unless otherwise noted. Medical history and AEs will be coded using the Medical Dictionary for Regulatory Activities (MedDRA) Version 19.0. Concomitant medications will be coded using the World Health Organization (WHO) Drug Dictionary (September, 2016).

3.4. Baseline Definitions

For all analyses, baseline will be defined as the most recent measurement prior to the first administration of study drug.

3.5. Methods of Pooling Data

Overall summaries of safety parameters will be presented by stage of enrollment for AML patient groups across all dose levels.

Efficacy analyses for patients with AML who received 12 µg/kg in Stage 2 will be conducted. Subgroup analyses by MRD status and line of therapy will also be performed.

3.6. Adjustments for Covariates

Due to small sample size, no formal statistical analyses that adjust for possible covariate effects are planned. Exploratory subgroup analyses will be performed for descriptive purposes, as described in [Section 3.8](#).

3.7. Multiple Comparisons/Multiplicity

Multiplicity is not of concern for this Phase 1 study.

3.8. Subgroup Analyses

Subgroup analyses will be performed for efficacy analyses by MRD status and line of therapy in study (First-Line or Relapsed/Refractory).

3.9. Withdrawals, Dropouts, Loss to Follow-up

At the discretion of the Sponsor, additional patients may be enrolled to supplement patient data compromised due to premature study dropout or other reasons.

3.10. Missing, Unused, and Spurious Data

In general, there will be no substitutions made to accommodate missing data points. All data recorded on the eCRF will be included in data listings that will accompany the CSR.

When tabulating AE data, partial dates will be handled as follows. If the day of the month is missing, the onset day will be set to the first day of the month unless it is the same month and year as study treatment. In this case, in order to conservatively report the event as treatment-emergent, the onset date will be assumed to be the first day of treatment. If the onset day and month are both missing, the day and month will be assumed to be January 1, unless the event occurred in the same year as the study treatment. In this case, the event onset will be set to the first day of treatment in order to conservatively report the event as treatment-emergent. A missing onset date will be set to the first day of treatment.

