4.4.2. Adverse Events

All AEs will be coded using the MedDRA coding system and displayed in tables and data listings using system organ class (SOC) and preferred term (PT).

Analyses of AEs will be performed for those events that are considered treatment-emergent, where treatment-emergent is defined per protocol as any AE with onset after the first administration of Tagraxofusp through 30 days after the last dose of Tagraxofusp, or any event that was present at baseline but worsened in intensity or was subsequently considered drug-related by the Investigator through 30 days after the last dose of Tagraxofusp.

The number and percentage of patients with any treatment-emergent AE (TEAE), with any TEAE assessed by the Investigator as related to treatment, with any TEAE with severity \geq Common Terminology Criteria for Adverse Events (CTCAE) Grade 3, with any SAE, with any AE leading to discontinuation of study treatment, and with any AE leading to dose modification will be summarized by dose group and overall. In these tabulations, each patient will contribute only once (ie, the most related occurrence or the most intense occurrence) to each of the incidence rates in the descriptive analysis, regardless of the number of episodes.

Treatment-emergent AEs summarized by patient incidence rates are not tabulated by severity or relationship to study treatment; therefore, in such tabulations, a patient contributes only once to the count for a given AE SOC or PT. For tabulations that include classification by relationship to study treatment, AEs with missing relationship will be considered related to study drug.

Adverse events of special interest (AESI's) will be determined using MedDRA version 19.0 standardized medical queries (SMQs), high-level terms, or PTs, as follows:

- Possible hypersensitivity events, based on the SMQ Hypersensitivity (broad search).
- Vascular capillary leak syndrome (CLS), based on the MedDRA SMQ [to be provided] in addition to PTs of hypoalbuminaemia, blood albumin decreased, and proteinuria.
- Possible drug-induced liver injury events, based on the SMQ drug-related hepatic disorders (broad search).

Summary tables of AESIs produced will report AESIs as follows:

- AESIs overall and by PT,
- AESIs by PT overall and by grouped cycle (Cycle 1, Cycles 2-4, Cycles \geq 5),
- \geq 3 Grade AESIs overall and by PT,
- Serious AESIs overall and by PT,
- AESIs resulting in drug interruption overall and by PT,

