4.4.2.1. Capillary Leak Syndrome

In addition to the summaries described in [Section 4.4.2](#), summaries will be provided that include:

- Summary of number and grade of CLS events, exposure to Tagraxofusp prior to onset of CLS, and time to first onset and time to resolution of CSL events.

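### Incomplete AE dates imputed to the first dose suit the treatment-emergent flag, but they bias CLS timing and possibly the by-cycle AESI table

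*SAP*

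**What the plan says.** SAP section 3.10 gives the rules for incomplete onset dates and introduces them as applying to the tabulation of AE data in general.

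- **Day missing.** The rule begins "If the day of the month is missing, the onset day will be set to the first day of the month unless it is the" and then excepts a month and year that coincide with study treatment. In that case, "in order to conservatively report the event as treatment-emergent, the onset date will be assumed to be the first day of treatment". The SAP does not say whether this means the month of the first dose or any month on treatment.
- **Day and month missing.** The default is 1 January. If the year coincides with study treatment, "the event onset will be set to the first day of treatment in order to conservatively report the event as treatment-emergent".
- **Date wholly missing.** "A missing onset date will be set to the first day of treatment".

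Two planned outputs depend on when an event began. SAP section 4.4.2 lists "AESIs by PT overall and by grouped cycle (Cycle 1, Cycles 2-4", with a third group from Cycle 5 onward. SAP section 4.4.2.1 summarizes "exposure to Tagraxofusp prior to onset of CLS, and time to first onset and time to resolution of CSL events". Neither section sets its own rule for imputed dates. The SAP provides no category for an unknown cycle, makes no use of the AE end date, and does not exclude imputed onsets from timing summaries.

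**The concern.** The stated reason for choosing the first dose date is to make sure that the event counts as treatment-emergent. For that purpose the choice errs in the safe direction. For timing it does not: an event of unknown date is given the earliest possible on-treatment onset, so the error always has the same sign.

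Safety characterization is a primary objective, and Protocol section 3.6.3 names experience with repeated cycles as an aim of the study. When CLS occurs, and after how much drug, is part of that. Protocol section 7.5.5.1 describes CLS as arising 3 to 8 days after treatment starts, so an onset on the first dose day also fits poorly with the protocol's own description.

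**Working it through.** The plan states no figure on this point, so there is none to reproduce. The check applies the rule to the calendar.

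**Inputs.** Cycle of 28 days (SAP 1.2.1). Five infusions per cycle and up to six cycles (Protocol 7.5.2). Treatment-emergent window to 30 days after the last dose (SAP 4.4.2). Enrolment of 18 + 9 = 27 (SAP 3.1).

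**Assumptions.** No delays; true onset equally likely on any day in the window; first dose equally likely on any day of a 365-day year. The resulting shares describe where an undated event could lie. They do not estimate how often dates will be incomplete.

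**1. Date wholly missing.** The window closes on Day (cycles − 1) × 28 + 5 + 30. Follow-up after the last dose is counted with the last cycle.

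| Cycles given | Window closes | Days in Cycle 1 | Days in later cycles |
|---|---|---|---|
| 2 | Day 63 | 28/63 = 44% | 35/63 = 56% |
| 4 | Day 119 | 28/119 = 24% | 91/119 = 76% |
| 6 | Day 175 | 28/175 = 16% | 147/175 = 84% |

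With six cycles the 84% splits into 84/175 = 48% in Cycles 2-4 and 63/175 = 36% in Cycle 5 or later. All of these are tabulated on the first dose date. The largest shift is 175 − 1 = 174 days.

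**2. Only the year known, same year as first dose (six cycles).** Enumerating every first-dose date and every onset day in that calendar year gives 20% in Cycle 1, 51% in Cycles 2-4 and 29% in Cycle 5 or later. About 80% of possible days are therefore moved into Cycle 1.

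**3. Only the year known, treatment crossing a year end.** Take a first dose on 16 October and an event known to fall in the next year. The earliest possible onset is 1 January, which is 15 + 30 + 31 + 1 = 77 days after the first dose, or Day 78 in Cycle 3. If the exception covers any treatment year, onset still becomes 16 October, which contradicts the recorded year.

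**4. Only the day missing.**

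- Exception limited to the first-dose month: shift of at most 30 days, and 54 of 5,738 enumerated days (0.9%) leave Cycle 1. Dates in later months go to the first of that month; about 18% of those possible days change cycle group.
- Exception covering any treatment month: every such date goes to the first dose, with errors of the kind in steps 1 and 2.

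**5. Direction.** Let s be the number of days from first dose to true onset, s ≥ 0. Imputation reduces time to onset by s and, where the end date is known, increases time to resolution by s. Example: first dose 16 January, true onset 22 May, only the year recorded. Then s = 126, and true onset is Day 127 in Cycle 5. If onset is calculated as a simple date difference (the SAP gives no formula), 126 days becomes 0. If all doses were given, prior exposure of 4 × 5 + 5 = 25 infusions becomes none. Time to resolution is 126 days too long.

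**6. Effect of one moved event on a table cell.** This depends on the denominator. Against all 27 patients it is 1/27 = 3.7 points. Against Stage 1 planned cohorts of 3 to 6 it is 1/6 = 17 to 1/3 = 33 points. The SAP does not give the dose-group denominators, so none of these is the effect in an identified planned table.

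**The case against.** The case for leaving the rule alone has real parts.

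- **A dated later month is probably handled already.** A reader might infer that an event known to be in month 4, with only the day missing, goes to the first dose. The default sends it to the first of that month. The exception is needed only where the first of the month might precede dosing, so its purpose favours the first-dose-month reading. What stands here is an ambiguity.
- **The link to cycle is not written down.** The SAP does not say that cycle group is derived from onset date. SAP section 3.11 tabulates data by recorded visit, but that concerns scheduled assessments. AEs are collected continuously (Protocol 10.2) and reported on their own form (Protocol 10.5). Visit-based assignment could protect the by-cycle table, but the SAP does not adopt it for AEs, and it would not supply a CLS onset time.
- **Badly dated CLS events should be rare.** Patients are seen on infusion days and contacted around Days 8, 15, 21 and 28, CLS leads to withheld doses, and monitors query missing data. This stands, and it limits the importance of the point.
- **A simple later-of rule does not cure the main cases.** The later of first dose and the first day of the known period still gives first dose for a wholly missing date and for a year-only date in the first-dose year. This stands, so those onsets must also be kept out of timing outputs.

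**Conclusion.** The point holds as a low-priority improvement. For wholly missing dates, and for year-only dates in the first-dose year, section 3.10 plainly assigns the first dose date, and nothing confines that date to the treatment-emergent flag. The CLS summary is directly exposed: onset and prior exposure too short, resolution too long. The grouped-cycle AESI table is exposed only if cycle comes from onset date. An individual error can reach 174 days with six on-time cycles, or more with delays. The total effect cannot be stated because the number of incomplete dates is not given; it is probably small.

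A reader might go further and infer that overall TEAE incidence is distorted, that all partial dates go to Cycle 1, or that the AST/ALT Kaplan-Meier curves are affected. The documents do not support these. The rule does not undercount TEAEs, the defaults are the first of the month and 1 January, and the AST/ALT analysis sits under laboratory data (SAP 4.4.3), so it presumably uses sample dates. Nor should 3.7 points be quoted as the effect: AESI tables are by dose group, and a patient who already has the same term in Cycle 1 would not change that cell.

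**What to change.** 1. In SAP section 3.10, tie the day-missing exception to the calendar month of the first dose, and the day-and-month-missing exception to its calendar year. Onset is then the later of the first dose and the first day of the known month or year, provided the known part does not exclude the first dose. A known later month or year is never overridden.
2. State that imputation to the first dose date serves only the treatment-emergent flag.
3. Exclude such onsets from the CLS onset, exposure and resolution summaries. In the grouped-cycle AESI table, assign them by the recorded eCRF visit or cycle, or show them in a cycle-unknown row. Give their number in a footnote to each output.

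The cost is a few SAP sentences and slightly fewer events in the timing summaries. No new data are needed, and these steps leave treatment-emergent status unchanged. If the AE end date is added as a bound, the SAP should say that an event ending before the first dose is not treatment-emergent; that addition does change the status of such events.
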